1. INTRODUCTION

This Statistical Analysis Plan (SAP) describes the analyses and presentation of all safety, tolerability and selected efficacy endpoints for the clinical study report (CSR) of the pooled AC-058B201 (core) and AC-058B202 (extension) studies.

For these analyses, the data for subjects in the core study is pooled with all data in the extension study. The pooled analyses described in this SAP focus on the period when subjects were treated with ponesimod, i.e., excluding the placebo period for those subjects who received placebo in the core study. The placebo data, however, includes certain disposition summaries to enable full traceability of subjects across the two studies.

Study data was initially collected in paper Case Report Forms (CRFs) and uploaded to a legacy database. Subsequently, on 9th August 2021, an electronic CRF (eCRF) was created and the study data was migrated to iMedidata RAVE EDC on 17th Nov. 2021.

Study Data Tabulation Model (SDTM) datasets are provided for both the core and extension and are considered the source data for the analyses. Throughout this SAP, SDTM201.XX refers to the SDTM domain XX for the core study, SDTM202.XX refers to the SDTM domain XX for the extension study, and SDTM.XX refers to the SDTM domain XX for either/both the core and extension studies.

The database lock date used for analyses described in this SAP will be specified in the Database Release Plan (DRP). All data (visits/occurrence dates) are planned to be entered in the database prior to this database lock date and will be included in the analyses.

Datasets and outputs related to the Covid-19 and Influenza Immunogenicity Analysis described in Appendices 11 and 12 respectively, as well as the Pharmacokinetics/Pharmacodynamics analysis described Sections 5.5.1 and 5.5.2, will be developed internally, whereas the rest of the analyses will be developed by a CRO.

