3. SAMPLE SIZE DETERMINATION

As described in the Section 1.2.2, the sample sizes in the various phases of the study are determined by the treatment pathways starting with the core study.

POPULATIONS (ANALYSIS SETS) FOR ANALYSIS 4.

Table 1: **Description of Analysis Sets**

Analysis Sets	Description
All Randomized Set (RND)	The randomized analysis set includes all participants who were randomized in the core study.
Ponesimod Analysis Set (PAS)	This set includes all subjects who received at least one dose of ponesimod at any time during the core and/or the extension study.
Echocardiography Analysis Set (ECHO)	This includes all subjects in the PAS who have at least one echocardiography assessment after first dose of ponesimod.
Optical Coherence Tomography Analysis Set (OCT)	This includes all subjects in the PAS who have at least one OCT assessment after first dose of ponesimod.

An overview of the different analysis sets and their usage is given in Table 2 below.

Usage of Analysis Sets Table 2:

Analyses/Data Displays	RND	PAS	ECHO	OCT
Disposition	✓	✓		
Demographic characteristics		~		
Baseline characteristics		~		
Medical history		~		
Previous and concomitant medications		 ✓ 		
Protocol deviations		√*		
Treatment exposure		~		
Efficacy: Relapse		~		
Efficacy: MRI		~		
Efficacy: Neurological		~		
Efficacy: Ophthalmological				 ✓
Safety: Holter ECG		✓		

Safety: Echocardiography		\checkmark	
Safety: All other endpoints	~		
All subject listings	~		

*Subset on subjects entering the extension study.

ECG = electrocardiogram; ECHO = Echocardiography analysis set; OCT = Optical coherence tomography analysis set; PAS = Ponesimod analysis set; RND = All-randomized analysis set.

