5.2.1.3. Subjects randomized/entered

The following variables are defined:

- **Randomized in the core study**: a subject is considered as randomized in the core study if randomization date and number are recorded in the core study. Randomization date is stored in SDTM201.DS.DSSTDTC where DS.DSDECOD='RANDOMIZED', randomization number is stored in SDTM201.DS.DSREFID When DS.DSTERM = RANDOMIZED. Treatment assignment is stored in SDTM.DM.ARM. Note: 2 subjects in the core study were randomized and not treated. These subjects will not be included in any analyses described in this SAP.
- **Randomized/entered TP1**: a subject is considered as randomized/entered in TP1 if they have a randomization/enrollment date entered for TP1. Randomization date is stored in SDTM202.DS.DSSTDTC where DS.DSSCAT='ENROLLMENT IN TP1'.
- **Randomized/entered TP2**: a subject is considered as randomized/entered in TP2 if they have a randomization/enrollment date entered for TP2. Randomization date is stored in SDTM202.DS.DSSTDTC where DS.DSSCAT='ENROLLMENT IN TP2'.
- Entered TP3: a subject is considered to have entered TP3 if they have a record in the study drug log (SDTM202.EC and SDTM202.SUPPEC) indicating transition to TP3.
- **Entered Follow-up Phase:** a subject is considered to have entered the Follow-up Phase if they have at least one Follow-up visit after EOT.

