5.2.1.6. Subject study completion status

A subject is considered to have completed study in either the core or the extension if they completed the EOS Visit as per protocol. This definition is independent of treatment completion, i.e., a subject can prematurely discontinue from treatment but complete the study.

A subject is considered to have completed the core study as per protocol if a study completion record is documented in SDTM202.DS, i.e., where DSSCAT='STUDY TERMINATION' and DSDECOD is equal to 'COMPLETED'. Date of completion is the date in DSSTDTC for this record.

A subject is considered to have prematurely discontinued from the core study if a permanent reason for study discontinuation or date of study discontinuation is documented in SDTM201.DS, i.e., where DSSCAT = 'STUDY TERMINATION' and DSDECOD is not equal to 'COMPLETED'. Date of core study discontinuation is the date in DSSTDTC for this record and reason for discontinuation is stored in DSDECOD.

Possible main reasons for premature discontinuation in the core study are 'Death', 'Withdrawal of subject's consent', 'Lost to follow-up' and 'Administrative reason'.

A subject is considered to have completed the extension study as per protocol if a study completion record is documented in SDTM202.DS, i.e., where DSSCAT = 'STUDY TERMINATION' and DSDECOD is equal to 'COMPLETED'. Date of completion is the date in DSSTDTC for this record. A subject is considered to have completed study per protocol in a given period if they entered the period and completed the extension study whilst in that period.

A subject who transitions to commercial study drug is considered to have completed the extension study as per protocol and if DSSCAT = 'STUDY TERMINATION' and DSDECOD is equal to

Statistical Analysis Plan AC-058B202

'APPROVED DRUG AVAILABLE FOR INDICATION' in SDTM202.DS. Date of completion is the date in DSSTDTC for this record.

A subject is considered to have prematurely discontinued from the extension study if a reason for premature study discontinuation or date of study discontinuation is documented in SDTM202.DS, i.e., where DSSCAT = 'STUDY TERMINATION' and DSDECOD is not equal to 'COMPLETED' or 'APPROVED DRUG AVAILABLE FOR INDICATION'. Date of extension study discontinuation is the date in DSSTDTC for this record and reason for discontinuation is stored in DSDECOD.

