Possible main reasons for premature discontinuation from the extension study are 'Death', 'Lost to follow-up', 'Withdrawal by Subject', 'Physician decision', 'Sponsor decision'. 'Withdrawal by Subject' is further categorized into: 'Tolerability related', 'Efficacy related', 'Other' and 'Not Known'. Physician decision is further categorized into: 'Adverse event', 'Lack of efficacy/Treatment failure', and 'Other'. Sponsor decision is further categorized into 'Study terminated', and 'Other'.

If the subject, investigator or sponsor decision reason is 'Other', the specific reason is captured in DS.DSTERM as free-text.

The following variables are defined for study completion/discontinuation:

- Completed the core study as per protocol;
- Prematurely discontinued study in the core;
- Reason for premature discontinuation in the core study;
- Completed the core study as per protocol and not entered in the extension;
- Completed TP1 as per protocol;
- Prematurely discontinued study in TP1;
- Reason for premature study discontinuation in TP1;
- Completed TP1 as per protocol and not entered in TP2;
- Completed TP2 as per protocol;
- Prematurely discontinued study in TP2;
- Reason for premature study discontinuation in TP2;
- Completed TP2 as per protocol and not entered in TP3;
- Completed TP3 as per protocol;
- Availability of commercial ponesimod in TP3*
- Prematurely discontinued study in TP3;
- Reason for premature study discontinuation in TP3;

*This will not be listed as a reason for premature study discontinuation as this is considered study completion as per protocol provided the subject had an EOS2 or EOS3 assessment.

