5.2.2. Display of Subject Disposition

The following subject disposition tables are created to summarize the treatment disposition across the different treatment periods:

- Subject disposition during the core study, by randomized treatment in the core study (RND);
- Subject disposition during TP3, by randomized treatment pathway in core/TP1/TP2 (PAS).

For each of these tables, the number of subjects randomized/enrolled, treated, completed treatment, interrupted treatment for planned pregnancy (TP2/TP3 only), restarted treatment after planned pregnancy (TP2/TP3 only), prematurely discontinued treatment, reason for premature discontinuation of treatment, completed study as per protocol, prematurely discontinued study, reason for premature study discontinuation, completed study in the treatment period as per protocol and did not enter the following treatment period (Core, TP1 and TP2 only) are summarized. Percentages are based on the number of subjects who were randomized in the treatment period. All tables include a total column. Percentages for treatment completion/discontinuation variables are based on the number of subjects treated in the treatment period; percentages for study completion/discontinuation variables are based on the number of subjects randomized in the treatment period. Study and treatment completion due to "Approved Drug Availabile for Indication" will be a subcategory of study/treatment completion in the tables under "Availability of commercial ponesimod".

An additional disposition table is created to summarize treatment disposition in AP3 on the PAS, by treatment period and treatment group and overall. For each treatment period (Core, TP1, TP2, TP3), the number of subjects randomized/enrolled, treated, completed treatment, prematurely discontinued treatment, completed study as per protocol, prematurely discontinued study, completed study in the treatment period as per protocol and did not enter the following treatment period (Core, TP1 and TP2 only), interrupted treatment for planned pregnancy (TP2 and TP3 only), restarted treatment after planned pregnancy (TP2 and TP3 only) are summarized. Study and treatment completion due to "Approved Drug Available for Indication" will be a subcategory of study/treatment completion in the tables under "Availability of commercial ponesimod".

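### SAP 5.2.1.6 reads completion of the core study from the extension dataset, and SAP 5.2.1.3 drops two randomized subjects from a table defined on all randomized: disposition errors only, cheap to correct

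*SAP*

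**What the plan says.** **Naming.** SAP section 1 fixes the prefixes: "SDTM201.XX refers to the SDTM domain XX for the core study, SDTM202.XX refers to the SDTM domain XX for the extension study".

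**Completion rules.** For the core, section 5.2.1.6 says "A subject is considered to have completed the core study as per protocol if a study completion record is documented in SDTM202.DS", requiring a STUDY TERMINATION record coded COMPLETED and taking that record's date as the completion date. Further down, the same section says "A subject is considered to have completed the extension study as per protocol if a study completion record is documented in SDTM202.DS", with the same two conditions. Premature core discontinuation, in between, is identified "if a permanent reason for study discontinuation or date of study discontinuation is documented in SDTM201.DS".

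**Where the status is used.** Section 5.2.1.6 lists the variable "Completed the core study as per protocol and not entered in the extension". Section 5.2.2 plans a table described as "Subject disposition during the core study, by randomized treatment in the core study (RND"). It also plans a table on the Ponesimod Analysis Set (PAS), by treatment period and treatment group. Both show core study completion and completers who did not go on.

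**Population.** For RND, Table 1 in section 4 states: "The randomized analysis set includes all participants who were randomized in the core study". Of the two subjects randomized but not treated, section 5.2.1.3 says: "These subjects will not be included in any analyses described in this SAP".

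**The concern.** The core and extension completion rules are the same rule, so as written the SAP has no definition of completing the core. The SAP says it keeps placebo subjects in certain disposition summaries so that everyone can be traced across the two studies (sections 1 and 5.1.9). The row that shows who finished the core and stopped there is the one this rule empties. Section 1 also assigns most of the programming to a CRO, so the written derivation is what will be coded.

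The second conflict is smaller and independent. One table cannot both include all randomized subjects and leave two of them out.

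At stake is the accuracy of the participant flow in the final report. No treatment comparison depends on it.

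**Working it through.** **1. Neighbouring core derivations.**

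| Core item | SAP section | Source |
|---|---|---|
| End-of-study date | 5.1.1 | SDTM201.DS |
| Treatment completion | 5.2.1.5 | SDTM201.DS |
| Treatment discontinuation | 5.2.1.5 | SDTM201.DS |
| Study discontinuation | 5.2.1.6 | SDTM201.DS |
| **Study completion** | **5.2.1.6** | **SDTM202.DS** |

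Only the last row departs from the pattern. SAP Appendix 2, which lists changes and clarifications, does not mention it.

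**2. Applying the rule to each pathway.** Core completer means COMPLETED in the stated dataset. Core discontinuer means any other termination code in SDTM201.DS.

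| Core outcome | Entered extension | Extension outcome | As written: completer / discontinuer | From SDTM201.DS: completer / discontinuer |
|---|---|---|---|---|
| Completed | No | none | No / No | Yes / No |
| Completed | Yes | Completed | Yes / No | Yes / No |
| Completed | Yes | Switched to commercial drug | No / No | Yes / No |
| Completed | Yes | Left early | No / No | Yes / No |
| Left early | No | none | No / Yes | No / Yes |

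Four pathways complete the core, and the written rule recognizes one of them.

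**3. Consequences.**
- Non-rollover requires core completion and no entry to the extension. A subject who did not enter has no extension end-of-study date (SAP 5.1.1 sets it to missing), so the two conditions cannot both hold. The count is 0 in every arm.
- Core completers plus core discontinuers fall short of the number randomized by everyone in the first, third and fourth rows.
- Subjects in the second row get the extension termination date as their core completion date, which conflicts with the core end-of-study date in SAP 5.1.1. The protocol (3.1.1) allows up to 649 weeks in the extension.

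**4. Which tables.** The core study-completion and non-rollover rows are affected in the RND core table and in the PAS by-period table. Placebo subjects who never entered the extension received no ponesimod and are outside the PAS, so only the RND table can show them.

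**5. The two untreated subjects.** Protocol 1.3.2.3 gives 464 randomized, of whom all but two, both in the 20 mg arm, were treated. SAP 5.2.1.3 also gives two.
- RND as defined: 464. With the exclusion: 464 − 2 = 462.
- Overall difference: 2 / 464 = 0.43%.
- Within the 20 mg arm: neither document gives the arm size. Equal allocation implies 464 / 4 = 116, and 2 / 116 = 1.72%. An assumed arm size of 110 to 122 gives 1.82% to 1.64%.

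Section 5.2.2 bases study-completion percentages on the number randomized, so the choice moves that denominator. Table 2 in section 4 uses RND for disposition only. Applying the exclusion there would leave the all-randomized set with no use as defined.

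**The case against.** The strongest reply is that this is one wrong digit. The opening sentence of 5.2.1.6 states the intent (completing the end-of-study visit per protocol, in either study), every adjacent rule points to SDTM201, and a programmer would see that completers and discontinuers do not add up. That stands as to intent. It does not remove the need for a correction, because the operative sentence is explicit and nothing in the SAP overrides it.

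The reply also limits the importance of the point. A reader might infer any of the following, and the documents do not support them:
- *That the error hides how the pooled long-term cohort was selected.* The PAS (SAP section 4) takes anyone with at least one ponesimod dose in either study, so ponesimod-treated subjects who did not roll over stay in the analysis up to their core end-of-study date. Entry to the extension depends on completing core treatment at Week 24 (protocol 3.4.2). Core treatment completion and TP1 entry are derived from the right datasets (SAP 5.2.1.5 and 5.2.1.3).
- *That the RND table is the only place where non-rollover appears.* The PAS by-period table shows it too. The RND table is unique only for placebo.
- *That a known share of completers will be misclassified.* Neither document gives extension outcomes, so no percentage can be stated.
- *That an output is already wrong.* The text shows a wrong specification. It says nothing about what was programmed.
- *That the two untreated subjects distort the core-to-extension step.* They took no study drug, could not meet the entry criterion, and so affect no rollover count.

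**Conclusion.** The core completion rule is wrong as specified. The zero non-rollover count follows from the wording alone, given that subjects outside the extension have no extension termination record, as SAP 5.1.1 implies. The number misclassified among those who did enter cannot be estimated from the documents.

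The exclusion of the two untreated subjects contradicts the RND table. It is worth two subjects, and only the 20 mg percentages depend on an assumed arm size.

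Both matter for disposition and traceability only. Efficacy and safety analyses do not use core study-completion status, the analysis-period end dates rest on the core end-of-study date from SDTM201.DS, and untreated subjects are outside the PAS in any case. Low severity, but worth correcting because the correction is nearly free.

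**What to change.** 1. In SAP 5.2.1.6, change the source for core study completion from SDTM202.DS to SDTM201.DS, keeping the STUDY TERMINATION and COMPLETED conditions.
2. In the same section, define core completers who did not roll over as subjects with that SDTM201.DS record and no 'ENROLLMENT IN TP1' record in SDTM202.DS.
3. In SAP 5.2.1.3, limit the exclusion of the two untreated subjects to PAS analyses, so that the RND disposition table accounts for all 464.

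As a check on the programmed core table, completers plus discontinuers should account for every subject with a core termination record.

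Cost: three sentences in the SAP. The core termination records are already in SDTM201.DS, so no new data are needed.

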5.2.1.7. Time on study

Time on study (years) is derived for the ponesimod period of the core and extension studies combined (i.e., excluding placebo period) as (last study date – [date randomized in core study (if

randomized to ponesimod in the core study) or date randomized/entered in TP1 (if randomized to placebo in the core study and continuing to the extension study)] + 1 day)/365.25.

Time on study is categorized into the following intervals: ≤ 6 months, > 6 months and ≤ 1 year, > 1 year and ≤ 2 years, > 2 years and ≤ 3 years, > 3 years and ≤ 4 years, > 4 years and ≤ 5 years, > 5 years and ≤ 6 years, > 6 years and ≤ 7 years, > 7 years and ≤ 8 years, > 8 years and ≤ 9 years, > 9 years and ≤ 10 years, > 10 years and ≤ 11 years, > 11 years and ≤ 12 years, > 12 years

5.2.2. Display of Subject Disposition

The following subject disposition tables are created to summarize the treatment disposition across the different treatment periods:

- Subject disposition during the core study, by randomized treatment in the core study (RND);
- Subject disposition during TP3, by randomized treatment pathway in core/TP1/TP2 (PAS).

For each of these tables, the number of subjects randomized/enrolled, treated, completed treatment, interrupted treatment for planned pregnancy (TP2/TP3 only), restarted treatment after planned pregnancy (TP2/TP3 only), prematurely discontinued treatment, reason for premature discontinuation of treatment, completed study as per protocol, prematurely discontinued study, reason for premature study discontinuation, completed study in the treatment period as per protocol and did not enter the following treatment period (Core, TP1 and TP2 only) are summarized. Percentages are based on the number of subjects who were randomized in the treatment period. All tables include a total column. Percentages for treatment completion/discontinuation variables are based on the number of subjects treated in the treatment period; percentages for study completion/discontinuation variables are based on the number of subjects randomized in the treatment period. Study and treatment completion due to "Approved Drug Availabile for Indication" will be a subcategory of study/treatment completion in the tables under "Availability of commercial ponesimod".

An additional disposition table is created to summarize treatment disposition in AP3 on the PAS, by treatment period and treatment group and overall. For each treatment period (Core, TP1, TP2, TP3), the number of subjects randomized/enrolled, treated, completed treatment, prematurely discontinued treatment, completed study as per protocol, prematurely discontinued study, completed study in the treatment period as per protocol and did not enter the following treatment period (Core, TP1 and TP2 only), interrupted treatment for planned pregnancy (TP2 and TP3 only), restarted treatment after planned pregnancy (TP2 and TP3 only) are summarized. Study and treatment completion due to "Approved Drug Available for Indication" will be a subcategory of study/treatment completion in the tables under "Availability of commercial ponesimod".

A further overview summary of disposition pooled across treatment periods is created for AP3 on the PAS, by treatment group and overall, to summarize the number of subjects randomized to ponesimod at any time, treated, completed treatment, prematurely discontinued treatment, interrupted treatment for planned pregnancy, restarted treatment after planned pregnancy, , completed study as per protocol, prematurely discontinued from study, completed study during a treatment period and not continuing to the next treatment period. Study and treatment completion due to "Approved Drug Available for Indication" will be a subcategory of study/treatment completion in the tables under "Availability of commercial ponesimod". An overall summary of condensed reasons for premature treatment discontinuation is created for AP3 on the PAS, by treatment group and overall, with condensed reasons for discontinuation categorized as described in Table 5 below.

A Kaplan-Meier plot for time to premature treatment discontinuation is produced for AP3 on the PAS.

Reasons for treatment discontinuation and reasons for study discontinuation are presented in separate listings.

A listing of start and end dates of each treatment period, together with treatment group and actual treatment in each period, is provided.

Collected Reason/Sub-reason	Displayed Reason
Death	Death
Lost to follow-up	Lost to follow-up
Protocol-specified withdrawal	Protocol-specified withdrawal criterion met
criterion met	
Subject decision – tolerability related	Tolerability related/adverse event
Subject decision – efficacy related	Efficacy related
Subject decision – other	Withdrawal by subject (other/unknown)
Subject decision – not known	Withdrawal by subject (other/unknown)
Withdrawal by subject – tolerability	Tolerability related/adverse event
related	
Withdrawal by subject – efficacy	Efficacy related
related	
Withdrawal by subject – other	Withdrawal by subject (other/unknown)
Withdrawal by subject – not known	Withdrawal by subject (other/unknown)
Physician decision – adverse event	Tolerability related/adverse event
Physician decision – lack of	Efficacy related
efficacy/treatment failure	
Physician decision – other	Investigator decision (other/unknown)
Physician decision – not known	Investigator decision (other/unknown)
Sponsor decision	Sponsor decision
Administrative reason	Administrative/other/unknown
Adverse event	Tolerability related/adverse event
Withdrawal of subject's consent	Withdrawal of consent
Protocol violation	Protocol violation
Administrative/other	Administrative/other/unknown
Investigator's decision	Investigator decision (other/unknown)
Withdrawal of consent	Withdrawal of consent
Approved drug available for	Availability of commercial ponesimod
indication *	
Other/not known	Administrative/other/unknown

 Table 5:
 Condensed reasons for treatment discontinuation

*In compliance with the protocol, this will not be presented as one of the reasons for treatment discontinuation but will be listed as a sub-category under Treatment completion.

